#### **Has been changed to read:**

After each DMC meeting, the chair of the DMC will communicate its recommendations to the designated AbbVie Primary Contact, as described in the DMC charter. The AbbVie Primary Contact will triage the recommendations to either the AbbVie study team if the recommendation can be implemented without unblinded data review or the Internal Executive Review Committee (IERC) if unblinded data review is required. The DMC, IERC, SDAC, and ERAC membership and responsibilities will be documented in the DMC charter.

### **Section 9.2 Ethical Conduct of the Study**

#### **Add: new last paragraph**

In the event of a state of emergency due to the COVID-19 pandemic leading to difficulties in performing protocol-specified procedures, AbbVie will engage with study site personnel in an effort to ensure the safety of subjects, maintain protocol compliance, and minimize risks to the integrity of the study while trying to best manage subject continuity of care. This may include alternative methods for assessments (e.g., contact by phone or

virtual site visits), alternative locations (e.g., use of infusion centers), and the shipping of IP and/or supplies directly to subjects. In all cases, these alternative measures must be permitted by local regulations and the IRB/IEC. Investigators should notify AbbVie if any urgent safety measures are taken to protect the subjects against any immediate hazards.

### **Section 9.3 Subject Information and Consent**

#### **Add: new last paragraph**

Due to the COVID-19 pandemic, protocol modifications in addition to those outlined in this protocol may become necessary. If this situation arises, verbal consent may be added to the informed consent already included in this protocol. Verbal consent would need to be obtained prior to making adaptations or substantial changes in study conduct in accordance with local regulations.

### **Section 11.0 Data Quality Assurance**

#### **Add: new last paragraph**

During the COVID-19 pandemic, remote source document review of data may be employed if permitted by the local regulatory authority, the IRB/IEC, and the study site.

**Appendix C. Study Activities**

**Previously read:**

Dose	Year 1													
	Dose 1	Dose 2	Dose 3	Dose 4	Dose 5	Dose 6	Dose 7	Dose 8	Dose 9	Dose 10	Dose 11	Dose 12	Dose 13	Dose 14
Visits & Procedures a	Day 1/ Baseline	Wk 4	Wk 8	Wk 12	Wk 16	Wk 20	Wk 24	Wk 28	Wk 32	Wk 36	Wk 40	Wk 44	Wk 48	Wk 52
Subject/study partner ICF b	X													
Medical history update c	X													
Treatment assignment	X													
Physical examination	X d													X
Retinal imaging scan e														
Vital signs f	X	X	X	X	X	X	X	X	X	X	X	X	X	X
Body weight f	X	X	X	X	X	X	X	X	X	X	X	X	X	X
Neurological examination	X d			X			X							X
12-lead ECG	X d			X			X							X
Clinical laboratory tests	X d			X			X						X	
Brain MRI	X d			X			X						X	
Optional LP/CSF collection	X d												X	
Tau PET g	X d												X	
Blood sample for ABBV-8E12 assay	X d			X			X						X	
ADA sample	X d			X			X						X	
Plasma and serum biomarker sample	X d			X			X						X	

Dose	Year 1													
	Dose 1	Dose 2	Dose 3	Dose 4	Dose 5	Dose 6	Dose 7	Dose 8	Dose 9	Dose 10	Dose 11	Dose 12	Dose 13	Dose 14
Visits & Procedures a	Day 1/ Baseline	Wk 4	Wk 8	Wk 12	Wk 16	Wk 20	Wk 24	Wk 28	Wk 32	Wk 36	Wk 40	Wk 44	Wk 48	Wk 52
Optional PG DNA and RNA sample h	X d			X			X						X	
Administer IV study drug a	X	X	X	X	X	X	X	X	X	X	X	X	X	X
CDR i	X d						X						X	
RBANS i	X d												X	
ADCS-MCI-ADL-24 i	X d													X
EQ-5D-5L i	X													X
C-SSRS fi	X	X	X	X	X	X	X	X	X	X	X	X	X	X
Digital measurements of cognition, actigraphy, and sleep j	X j						X j						X j	
Concomitant medications review f	X	X	X	X	X	X	X	X	X	X	X	X	X	X
AE assessment f	X	X	X	X	X	X	X	X	X	X	X	X	X	X

Dose	Year 2												
	Dose 15	Dose 16	Dose 17	Dose 18	Dose 19	Dose 20	Dose 21	Dose 22	Dose 23	Dose 24	Dose 25	Dose 26	Dose 27
Visits & Procedures a	Wk 56	Wk 60	Wk 64	Wk 68	Wk 72	Wk 76	Wk 80	Wk 84	Wk 88	Wk 92	Wk 96	Wk 100	Wk 104
Subject/study partner ICF b													
Medical history update c													
Treatment assignment													
Physical examination													X
Retinal imaging scan c		X											
Vital signs f	X	X	X	X	X	X	X	X	X	X	X	X	X
Body weight f	X	X	X	X	X	X	X	X	X	X	X	X	X
Neurological examination					X						X		
12-lead ECG													X
Clinical laboratory tests					X						X		
Brain MRI					X						X		
Optional LP/CSF collection											X		
Tau PET g											X		
Blood sample for ABBV-8E12 assay					X						X		
ADA sample					X						X		
Plasma and serum biomarker sample					X						X		
Optional PG DNA and RNA sample h					X						X		
Administer IV study drug a	X	X	X	X	X	X	X	X	X	X	X	X	X

Dose	Year 2												
	Dose 15	Dose 16	Dose 17	Dose 18	Dose 19	Dose 20	Dose 21	Dose 22	Dose 23	Dose 24	Dose 25	Dose 26	Dose 27
Visits & Procedures a	Wk 56	Wk 60	Wk 64	Wk 68	Wk 72	Wk 76	Wk 80	Wk 84	Wk 88	Wk 92	Wk 96	Wk 100	Wk 104
CDR i					X						X		
RBANS i											X		
ADCS-MCI-ADL-24 i													X
EQ-5D-5L i													X
C-SSRS f,i					X						X		X
Digital measurements of cognition, actigraphy, and sleep j				X j						X j			
Concomitant medications review f	X	X	X	X	X	X	X	X	X	X	X	X	X
AE assessment f	X	X	X	X	X	X	X	X	X	X	X	X	X

Dose	Year 3												
	Dose 28	Dose 29	Dose 30	Dose 31	Dose 32	Dose 33	Dose 34	Dose 35	Dose 36	Dose 37	Dose 38	Dose 39	Dose 40
Visits & Procedures a	Wk 108	Wk 112	Wk 116	Wk 120	Wk 124	Wk 128	Wk 132	Wk 136	Wk 140	Wk 144	Wk 148	Wk 152	Wk 156
Subject/study partner ICF b													
Medical history update c													
Treatment assignment													
Physical examination													X
Retinal imaging scan c													
Vital signs f	X	X	X	X	X	X	X	X	X	X	X	X	X
Body weight f	X	X	X	X	X	X	X	X	X	X	X	X	X
Neurological examination				X						X			
12-lead ECG													X
Clinical laboratory tests										X			
Brain MRI				X						X			
Optional LP/CSF collection													
Tau PET g										X			
Blood sample for ABBV-8E12 assay				X						X			
ADA sample				X						X			
Plasma and serum biomarker sample				X						X			
Optional PG DNA and RNA sample h				X						X			
Administer IV study drug a	X	X	X	X	X	X	X	X	X	X	X	X	X

Dose	Year 3												
	Dose 28	Dose 29	Dose 30	Dose 31	Dose 32	Dose 33	Dose 34	Dose 35	Dose 36	Dose 37	Dose 38	Dose 39	Dose 40
Visits & Procedures a	Wk 108	Wk 112	Wk 116	Wk 120	Wk 124	Wk 128	Wk 132	Wk 136	Wk 140	Wk 144	Wk 148	Wk 152	Wk 156
CDR i				X						X			
RBANS i										X			
ADCS-MCI-ADL-24 i													X
EQ-5D-5L i													X
C-SSRS fi				X						X			X
Digital measurements of cognition, actigraphy, and sleep j			X j						X j				
Concomitant medications review f	X	X	X	X	X	X	X	X	X	X	X	X	X
AE assessment f	X	X	X	X	X	X	X	X	X	X	X	X	X

Dose	Year 4												
	Dose 41	Dose 42	Dose 43	Dose 44	Dose 45	Dose 46	Dose 47	Dose 48	Dose 49	Dose 50	Dose 51	Dose 52	Dose 53
Visits & Proceduresa	Wk 160	Wk 164	Wk 168	Wk 172	Wk 176	Wk 180	Wk 184	Wk 188	Wk 192	Wk 196	Wk 200	Wk 204	Wk 208
Subject/study partner ICF b													
Medical history update c													
Treatment assignment													
Physical examination													X
Retinal imaging scan c													
Vital signs f	X	X	X	X	X	X	X	X	X	X	X	X	X
Body weight f	X	X	X	X	X	X	X	X	X	X	X	X	X
Neurological examination			X						X				
12-lead ECG													X
Clinical laboratory tests									X				
Brain MRI			X						X				
Optional LP/CSF collection													
Tau PET g									X				
Blood sample for ABBV-8E12 assay			X						X				
ADA sample			X						X				
Plasma and serum biomarker sample			X						X				
Optional PG DNA and RNA sample h			X						X				
Administer IV study drug a	X	X	X	X	X	X	X	X	X	X	X	X	X

Dose	Year 4												
	Dose 41	Dose 42	Dose 43	Dose 44	Dose 45	Dose 46	Dose 47	Dose 48	Dose 49	Dose 50	Dose 51	Dose 52	Dose 53
Visits & Procedures a	Wk 160	Wk 164	Wk 168	Wk 172	Wk 176	Wk 180	Wk 184	Wk 188	Wk 192	Wk 196	Wk 200	Wk 204	Wk 208
CDR i			X						X				
RBANS i									X				
ADCS-MCI-ADL-24 i													X
EQ-5D-5L i													X
C-SSRS fi			X						X				X
Digital measurements of cognition, actigraphy, and sleep i		X i						X i					
Concomitant medications review f	X	X	X	X	X	X	X	X	X	X	X	X	X
AE assessment f	X	X	X	X	X	X	X	X	X	X	X	X	X

Dose	Year 5												Wk 260/ Study Completion PD Visit	20 Wk Post-Last Dose k Follow- Up Visit
	Dose 54	Dose 55	Dose 56	Dose 57	Dose 58	Dose 59	Dose 60	Dose 61	Dose 62	Dose 63	Dose 64	Dose 65		
Visits & Procedures a	Wk 212	Wk 216	Wk 220	Wk 224	Wk 228	Wk 232	Wk 236	Wk 240	Wk 244	Wk 248	Wk 252	Wk 256		
Subject/study partner ICF b														
Medical history update c														
Treatment assignment														
Physical examination													X	
Retinal imaging scan c													X	
Vital signs f	X	X	X	X	X	X	X	X	X	X	X	X	X	X
Body weight f	X	X	X	X	X	X	X	X	X	X	X	X	X	
Neurological examination		X						X					X	X
12-lead ECG													X	
Clinical laboratory tests								X					X	X
Brain MRI		X						X					X	X
Optional LP/CSF collection													X	
Tau PET g													X	
Blood sample for ABBV-8E12 assay		X						X					X	X
ADA sample		X						X					X	X
Plasma and serum biomarker sample		X						X					X	X

Dose	Year 5												Wk 260/ Study Completion PD Visit	20 Wk Post-Last Dose k Follow- Up Visit
	Dose 54	Dose 55	Dose 56	Dose 57	Dose 58	Dose 59	Dose 60	Dose 61	Dose 62	Dose 63	Dose 64	Dose 65		
Visits & Procedures a	Wk 212	Wk 216	Wk 220	Wk 224	Wk 228	Wk 232	Wk 236	Wk 240	Wk 244	Wk 248	Wk 252	Wk 256		
Optional PG DNA and RNA sample h		X						X					X	
Administer IV study drug a	X	X	X	X	X	X	X	X	X	X	X	X		
CDR i		X						X					X	X
RBANS i								X					X	
ADCS-MCI-ADL-24 i													X	
EQ-5D-5L i													X	X
C-SSRS fi		X						X					X	X
Digital measurements of cognition, actigraphy, and sleep j	X j						X j					X j		
Concomitant medications review f	X	X	X	X	X	X	X	X	X	X	X	X	X	X
AE assessment f	X	X	X	X	X	X	X	X	X	X	X	X	X	X

Wk = Week

- Study drug will be administered on Day 1/Baseline visit, and then every 4 weeks thereafter until 1 of the discontinuation criteria is met, until the sponsor discontinues the study, or until the study reaches completion. Visits during the Treatment Period may be scheduled within  $\pm 4$  days. All dosing visits may be completed over 2 consecutive days at the discretion of the investigator with the second day to include the start and end of the infusion.
- Subject informed consent, or as applicable, legally authorized representative informed consent and subject assent, and study partner informed consent must be obtained prior to any Study M15-570 specific procedures being completed.

- c. Review medical history to confirm subject does not meet exclusion criteria prior to enrollment.
- d. Not required if procedure was conducted during the Week 96 visit in Study M15-566. A repeat assessment/procedure may be required based on discussion with the TA MD if more than 4 weeks have passed since the Week 96 visit.
- e. Exploratory eye test for AD pathology may be conducted at participating sites and will be performed at Weeks 60 and 260 or Premature Discontinuation.
- f. Vital signs, body weight, C-SSRS, concomitant medications review and AE assessment to be completed prior to administration of infusion.
- g. Subjects who did not complete tau PET imaging at Day 1/Baseline will have tau PET imaging performed at subsequent visits only after discussion with TA MD. Tau PET imaging will only be collected for subjects at sites selected to participate in the tau PET assessment.
- h. Optional pharmacogenetic DNA and RNA samples require consent. Verify consent prior to sample collection.
- i. The recommended order of administration is CDR followed by RBANS. When applicable, ADCS-MCI-ADL-24, EQ-5D-5L, and C-SSRS may be subsequently administered/assessed in any order prior to study drug administration.
- j. Start of collection period for digital measures of cognition, actigraphy, and sleep. Detailed instructions and other considerations will be provided in a separate manual.
- k. Post-treatment follow-up to occur approximately 20 weeks after the Completion or Premature Discontinuation (PD) visit.

Note: for subjects who prematurely discontinue the study, safety and efficacy assessments may be conducted remotely (for example, via telephone), where applicable.

**Has been changed to read:**

Dose	Year 1													
	Dose 1	Dose 2	Dose 3	Dose 4	Dose 5	Dose 6	Dose 7	Dose 8	Dose 9	Dose 10	Dose 11	Dose 12	Dose 13	Dose 14
Visits & Procedures a	Day 1/ Baseline	Wk 4	Wk 8	Wk 12	Wk 16	Wk 20	Wk 24	Wk 28	Wk 32	Wk 36	Wk 40	Wk 44	Wk 48	Wk 52
Subject/study partner ICF b	X													
Medical history update c	X													
Treatment assignment	X													
Physical examination	X d													X
Vital signs e	X	X	X	X	X	X	X	X	X	X	X	X	X	X
Body weight e	X	X	X	X	X	X	X	X	X	X	X	X	X	X
Neurological examination	X d			X			X							X
12-lead ECG	X d			X			X							X
Clinical laboratory tests	X d			X			X						X	
Brain MRI	X d			X			X						X	
Optional LP/CSF collection	X d												X	
Tau PET f	X d												X	
Blood sample for ABBV-8E12 assay	X d			X			X						X	
ADA sample	X d			X			X						X	
Plasma and serum biomarker sample	X d			X			X						X	
Optional PG DNA and RNA sample g	X d			X			X						X	

Dose	Year 1													
	Dose 1	Dose 2	Dose 3	Dose 4	Dose 5	Dose 6	Dose 7	Dose 8	Dose 9	Dose 10	Dose 11	Dose 12	Dose 13	Dose 14
Visits & Proceduresa	Day 1/ Baseline	Wk 4	Wk 8	Wk 12	Wk 16	Wk 20	Wk 24	Wk 28	Wk 32	Wk 36	Wk 40	Wk 44	Wk 48	Wk 52
Administer IV study drug a	X	X	X	X	X	X	X	X	X	X	X	X	X	X
CDR h	X d						X						X	
RBANS h	X d												X	
ADCS-MCI-ADL-24 h	X d													X
EQ-5D-5L h	X													X
C-SSRS e,h	X d	X	X	X	X	X	X	X	X	X	X	X	X	X
Concomitant medications review c	X	X	X	X	X	X	X	X	X	X	X	X	X	X
AE assessment c	X	X	X	X	X	X	X	X	X	X	X	X	X	X

Dose	Year 2												
	Dose 15	Dose 16	Dose 17	Dose 18	Dose 19	Dose 20	Dose 21	Dose 22	Dose 23	Dose 24	Dose 25	Dose 26	Dose 27
Visits & Procedures a	Wk 56	Wk 60	Wk 64	Wk 68	Wk 72	Wk 76	Wk 80	Wk 84	Wk 88	Wk 92	Wk 96	Wk 100	Wk 104
Subject/study partner ICF b													
Medical history update c													
Treatment assignment													
Physical examination													X
Vital signs c	X	X	X	X	X	X	X	X	X	X	X	X	X
Body weight c	X	X	X	X	X	X	X	X	X	X	X	X	X
Neurological examination					X						X		
12-lead ECG													X
Clinical laboratory tests					X						X		
Brain MRI					O						X		
Optional LP/CSF collection											X		
Tau PET f											X		
Blood sample for ABBV-8E12 assay					X						X		
ADA sample					X						X		
Plasma and serum biomarker sample					X						X		
Optional PG DNA and RNA sample g					X						X		
Administer IV study drug a	X	X	X	X	X	X	X	X	X	X	X	X	X
CDR h					X						X		

Dose	Year 2												
	Dose 15	Dose 16	Dose 17	Dose 18	Dose 19	Dose 20	Dose 21	Dose 22	Dose 23	Dose 24	Dose 25	Dose 26	Dose 27
Visits & Procedures a	Wk 56	Wk 60	Wk 64	Wk 68	Wk 72	Wk 76	Wk 80	Wk 84	Wk 88	Wk 92	Wk 96	Wk 100	Wk 104
RBANS h											X		
ADCS-MCI-ADL-24 h													X
EQ-5D-5L h													X
C-SSRS e,h					X						X		X
Concomitant medications review c	X	X	X	X	X	X	X	X	X	X	X	X	X
AE assessment c	X	X	X	X	X	X	X	X	X	X	X	X	X

Dose	Year 3												
	Dose 28	Dose 29	Dose 30	Dose 31	Dose 32	Dose 33	Dose 34	Dose 35	Dose 36	Dose 37	Dose 38	Dose 39	Dose 40
Visits & Procedures a	Wk 108	Wk 112	Wk 116	Wk 120	Wk 124	Wk 128	Wk 132	Wk 136	Wk 140	Wk 144	Wk 148	Wk 152	Wk 156
Subject/study partner ICF b													
Medical history update c													
Treatment assignment													
Physical examination													X
Vital signs c	X	X	X	X	X	X	X	X	X	X	X	X	X
Body weight c	X	X	X	X	X	X	X	X	X	X	X	X	X
Neurological examination				X						X			
12-lead ECG													X
Clinical laboratory tests										X			
Brain MRI				O						X			
Optional LP/CSF collection													
Tau PET f										X			
Blood sample for ABBV-8E12 assay				X						X			
ADA sample				X						X			
Plasma and serum biomarker sample				X						X			
Optional PG DNA and RNA sample g				X						X			
Administer IV study drug a	X	X	X	X	X	X	X	X	X	X	X	X	X
CDR h				X						X			

Dose	Year 3												
	Dose 28	Dose 29	Dose 30	Dose 31	Dose 32	Dose 33	Dose 34	Dose 35	Dose 36	Dose 37	Dose 38	Dose 39	Dose 40
Visits & Procedures a	Wk 108	Wk 112	Wk 116	Wk 120	Wk 124	Wk 128	Wk 132	Wk 136	Wk 140	Wk 144	Wk 148	Wk 152	Wk 156
RBANS h										X			
ADCS-MCI-ADL-24 h													X
EQ-5D-5L h													X
C-SSRS e,h				X						X			X
Concomitant medications review c	X	X	X	X	X	X	X	X	X	X	X	X	X
AE assessment c	X	X	X	X	X	X	X	X	X	X	X	X	X

Dose	Year 4												
	Dose 41	Dose 42	Dose 43	Dose 44	Dose 45	Dose 46	Dose 47	Dose 48	Dose 49	Dose 50	Dose 51	Dose 52	Dose 53
Visits & Proceduresa	Wk 160	Wk 164	Wk 168	Wk 172	Wk 176	Wk 180	Wk 184	Wk 188	Wk 192	Wk 196	Wk 200	Wk 204	Wk 208
Subject/study partner ICF b													
Medical history update c													
Treatment assignment													
Physical examination													X
Vital signs c	X	X	X	X	X	X	X	X	X	X	X	X	X
Body weight c	X	X	X	X	X	X	X	X	X	X	X	X	X
Neurological examination			X						X				
12-lead ECG													X
Clinical laboratory tests									X				
Brain MRI			O						X				
Optional LP/CSF collection													
Tau PET f									X				
Blood sample for ABBV-8E12 assay			X						X				
ADA sample			X						X				
Plasma and serum biomarker sample			X						X				
Optional PG DNA and RNA sample g			X						X				
Administer IV study drug a	X	X	X	X	X	X	X	X	X	X	X	X	X
CDR h			X						X				

Dose	Year 4												
	Dose 41	Dose 42	Dose 43	Dose 44	Dose 45	Dose 46	Dose 47	Dose 48	Dose 49	Dose 50	Dose 51	Dose 52	Dose 53
Visits & Procedures a	Wk 160	Wk 164	Wk 168	Wk 172	Wk 176	Wk 180	Wk 184	Wk 188	Wk 192	Wk 196	Wk 200	Wk 204	Wk 208
RBANS h									X				
ADCS-MCI-ADL-24 h													X
EQ-5D-5L h													X
C-SSRS e,h			X						X				X
Concomitant medications review c	X	X	X	X	X	X	X	X	X	X	X	X	X
AE assessment c	X	X	X	X	X	X	X	X	X	X	X	X	X

Dose	Year 5												Wk 260/ Study Completion PD Visit	20 Wk Post-Last Dose  Follow- Up Visit
	Dose 54	Dose 55	Dose 56	Dose 57	Dose 58	Dose 59	Dose 60	Dose 61	Dose 62	Dose 63	Dose 64	Dose 65		
Visits & Proceduresa	Wk 212	Wk 216	Wk 220	Wk 224	Wk 228	Wk 232	Wk 236	Wk 240	Wk 244	Wk 248	Wk 252	Wk 256		
Subject/study partner ICF b														
Medical history update c														
Treatment assignment														
Physical examination													X	
Vital signs c	X	X	X	X	X	X	X	X	X	X	X	X	X	X
Body weight c	X	X	X	X	X	X	X	X	X	X	X	X	X	
Neurological examination		X						X					X	X
12-lead ECG													X	
Clinical laboratory tests								X					X	X
Brain MRI		O						X					X	X
Optional LP/CSF collection													X	
Tau PET f													X	
Blood sample for ABBV-8E12 assay		X						X					X	X
ADA sample		X						X					X	X
Plasma and serum biomarker sample		X						X					X	X
Optional PG DNA and RNA sample g		X												X

Dose	Year 5												Wk 260/ Study Completion PD Visit	20 Wk Post-Last Dose  Follow- Up Visit
	Dose 54	Dose 55	Dose 56	Dose 57	Dose 58	Dose 59	Dose 60	Dose 61	Dose 62	Dose 63	Dose 64	Dose 65		
Visits & Procedures a	Wk 212	Wk 216	Wk 220	Wk 224	Wk 228	Wk 232	Wk 236	Wk 240	Wk 244	Wk 248	Wk 252	Wk 256		
Administer IV study drug a	X	X	X	X	X	X	X	X	X	X	X	X		
CDR h		X						X					X	X
RBANS h								X					X	
ADCS-MCI-ADL-24 h													X	
EQ-5D-5L h													X	X
C-SSRS e,h		X						X					X	X
Concomitant medications review c	X	X	X	X	X	X	X	X	X	X	X	X	X	X
AE assessment c	X	X	X	X	X	X	X	X	X	X	X	X	X	X

O = Optional; Wk = Week

- Study drug will be administered on Day 1/Baseline visit, and then every 4 weeks thereafter until 1 of the discontinuation criteria is met, until the sponsor discontinues the study, or until the study reaches completion. Visits during the Treatment Period may be scheduled within  $\pm$  4 days. All dosing visits may be completed over 2 consecutive days at the discretion of the investigator with the second day to include the start and end of the infusion.
- Subject informed consent, or as applicable, legally authorized representative informed consent and subject assent, and study partner informed consent must be obtained prior to any Study M15-570 specific procedures being completed.
- Review medical history to confirm subject does not meet exclusion criteria prior to enrollment.
- Not required if procedure was conducted during the Week 96 visit in Study M15-566. A repeat assessment/procedure may be required based on discussion with the TA MD or designee if subject is enrolling outside the 8 week window from the Week 92 visit in Study M15-566.
- Vital signs, body weight, C-SSRS, concomitant medications review and AE assessment to be completed to administration of infusion.
- Subjects who did not complete tau PET imaging through Study M15-566 and at Study M15-570 Day 1/Baseline will have tau PET imaging performed at subsequent visits only after discussion with TA MD or designee. Tau PET imaging will only be collected for subjects at sites selected to participate in the tau PET assessment.

- g. Optional pharmacogenetic DNA and RNA samples require consent. Verify consent prior to sample collection.
  - h. The recommended order of administration is CDR followed by RBANS. When applicable, ADCS-MCI-ADL-24, EQ-5D-5L, and C-SSRS may be subsequently administered/assessed in any order.
  - i. Post-treatment follow-up to occur approximately 20 weeks after the last dose.
- Note: For subjects who prematurely discontinue the study, safety and efficacy assessments may be conducted remotely (for example, via telephone), where applicable.

1.0 Purpose and Scope

This statistical programming plan (SPP) provides details to further elaborate some statistical methods as outlined in the statistical analyses plan (SAP) version 2.0 for M15-570 study. The document describes analysis conventions to guide the statistical programming work. The analysis will be completed by AbbVie Data and Statistical Sciences for tilavonemab (ABBV-8E12) Study Protocol M15-570.

2.0 Study-Specific Programming Guidelines

2.1 Definition of Analysis Sets

Data Set for Safety Analyses

The safety data set will contain data from Study M15-570 only, regardless of the treatment received in Study M15-566. Baseline for the safety data set will be the last observation before the first dose of tilavonemab in Study M15-570. If no baseline is recorded in Study M15-570, the last value in Study M15-566 will be used as the baseline.

2.2 Analysis Conventions

2.2.1 Statistical Significance

Unless otherwise specified, statistical tests will be two-sided for efficacy and safety analyses at 0.05 level.

2.2.2 Visit Definitions

Definition of Rx Day (Days Relative to the First Dose of Study Drug)

Rx Day is calculated for each time point as the number of days between the day of the first dose of study drug and the specific time point. For dates before the first dose date of study drug, Rx day = date of time point – first dose date; for dates on or after the first dose date of study drug, Rx day = date of time point – first dose date + 1. Thus, Rx Day is a negative value when the time point of interest is prior to the first study drug dose day; Rx Day is a positive value when

the time point of interest is on or after the first study drug dose day. There is no Rx Day 0. With this defined algorithm, the day of the first dose of study drug will be Rx Day 1.

RxEnd Day is calculated for each post-treatment time point as the number of days between the day of the last dose of study drug and the specific time point: RxEnd Day = date of time point – last dose date. With this defined algorithm, the day of the last dose of study drug will be RxEnd Day 0.

Definition of Baseline and Final Observation

For primary efficacy analyses on the ITT data set and for safety analyses on the safety data set of the Treatment Period, "baseline" shall refer to the last non-missing observation prior to the first dose of study drug of Study M15-570.

- If the duration between Day 1 of Study M15-570 and the last dose (Week 92) of Study M15-566 is less than or equal to 45 days and no M15-570 Day 1 visit data, vital sign, laboratory, MRI, and questionnaire data at visit Week 96 of Study M15-566 will be used as the baseline for Study M15-570. If M15-570 Day 1 visit data are available, Day 1 visit data will be used as the baseline.
- If the duration between Day 1 of M15-570 and the last dose (Week 92) of Study M15-566 is larger than 45 days, Day 1 visit data of Study M15-570 of vital sign, laboratory, MRI, and questionnaire data will be the baseline. If M15-570 Day 1 visit data are not available, the last available data from M15-566 will be used as the baseline.
- Day 1 visit data of M15-570 will always be the baseline of Study M15-570 for all other data (Adverse Event, ECG) and will not be impacted by the duration between Day 1 visit of Study M15-570 and Week 92 visit of Study M15-566.

For all safety analyses, "final" for the Treatment Period shall refer to the last non-missing observation in the Treatment Period but no more than 45 days after the last dose of the study drug for safety variables. The "final" for the post-treatment follow-up period for safety variables

shall refer to the last non-missing observation greater than 45 days but no more than 20 weeks after the last dose of study drug.

Definition of Analysis Windows

To perform longitudinal data analysis, observations that are obtained after the first day of study drug administration will be assigned to an analysis “Week” associated with the Rx Days that are corresponding to the observations. Unless otherwise specified, efficacy observations and safety observations no more than 45 days after the last dose of study drug will be included in analyses for the treatment period. Safety observations later than 45 days, but no more than 20 weeks, after the last dose of study drug will be included for the post-treatment follow-up period safety analysis. The intervals presented below for each scheduled visit (Rx Days X through Y) include both Rx Days X and Y. The nominal day for each scheduled post-baseline visit is 7 times “X” where “X” is visit week number. For example, the nominal day for Week 12 visit is $7 * 12 = 84$.

For measurements that are planned to be collected at Weeks 12, 24, 48, 72, 96, 144, 192, 240, and 260, i.e. clinical laboratory tests, observations will be mapped to an analysis “Week” according to the following windows defined by Rx day.

Week 12	Rx Days 2 through 126
Week 24	Rx Days 127 through 252
Week 48	Rx Days 253 through 420
Week 72	Rx Days 421 through 588
Week 96	Rx Days 589 through 840
Week 144	Rx Days 841 through 1176
Week 192	Rx Days 1177 through 1512
Week 240	Rx Days 1513 through 1750
Week 260	Rx Days > 1750

For measurements that are planned to be collected at Weeks 12, 24, 48, 72, 96, 120, 144, 168, 192, 216, 240 and 260, i.e. Brain MRI, observations will be mapped to an analysis “Week” according to the following windows defined by Rx day.

Week 12	Rx Days 2 through 126
Week 24	Rx Days 127 through 252

Week 48	Rx Days 253 through 420
Week 72	Rx Days 421 through 588
Week 96	Rx Days 589 through 756
Week 120	Rx Days 757 through 924
Week 144	Rx Days 925 through 1092
Week 168	Rx Days 1093 through 1260
Week 192	Rx Days 1261 through 1428
Week 216	Rx Days 1429 through 1596
Week 240	Rx Days 1597 through 1750
Week 260	Rx Days > 1750

For measurements that are planned to be collected at Weeks 4, 4n (n=2, 3, ...12), 52, 72, 96, 104, 120, 144, 156, 168, 192, 208, 216, 240 and 260, i.e. body weight and C-SSRS, observations will be mapped to an analysis "Week" according to the following windows defined by Rx day.

Week 4	Rx Days 2 through 42
Week 4n	Rx Days $7*((n-1)*4+2)+1$ through $7*(n*4+2)$
Week 52	Rx Days 351 through 434
Week 72	Rx Days 435 through 588
Week 96	Rx Days 589 through 700
Week 104	Rx Days 701 through 756
Week 120	Rx Days 757 through 924
Week 144	Rx Days 925 through 1050
Week 156	Rx Days 1051 through 1134
Week 168	Rx Days 1135 through 1260
Week 192	Rx Days 1261 through 1400
Week 208	Rx Days 1401 through 1484
Week 216	Rx Days 1485 through 1596
Week 240	Rx Days 1597 through 1750
Week 260	Rx Days > 1750

For safety assessments that are planned to be collected during post-treatment follow-up period, observations will be mapped to an analysis “Week” according to the following windows defined by RxEnd day.

Post-Treatment Week 20 $45 < \text{RxEnd Days} \leq 140$

If more than 1 observation is included in a visit time window, the non-missing observation closest to the nominal day will be used in analyses. If more than 1 observation occurs on the same day, the average will be calculated and used in analyses.

3.0 **Version History**

Table 1 SPP Version History Summary

Version	Date of Approval	Summary
1.0	10 Feb 2021	Initial version
2.0	30 Jul 2021	
 • Removed contents related to efficacy, biomarker analysis, PK analysis, and some safety sections to align with update SAP v2.0 for abbreviated CSR • Update TOC for abbreviated CSR

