#### **8.1.4 Safety Analyses**

Comparisons between treatment sequences (Study M15-566 and Study M15-570) of interest will not be performed.

All other safety assessments that are taken no more than 45 days after the last dose of study drug will be included in the safety evaluation of the Treatment Period, and all safety assessments that are taken more than 45 days but not more than 20 weeks after the last dose of study drug will be included in the safety evaluation for the Post-treatment Follow-up Visit.

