- Subjects who did not complete tau PET imaging through Study M15-566 and at Study M15-570 Day 1/Baseline will have tau PET imaging performed at subsequent visits only after discussion with TA MD or designee. Tau PET imaging will only be collected for subjects at sites selected to participate in the tau PET assessment.

- g. Optional pharmacogenetic DNA and RNA samples require consent. Verify consent prior to sample collection.
  - h. The recommended order of administration is CDR followed by RBANS. When applicable, ADCS-MCI-ADL-24, EQ-5D-5L, and C-SSRS may be subsequently administered/assessed in any order.
  - i. Post-treatment follow-up to occur approximately 20 weeks after the last dose.
- Note: For subjects who prematurely discontinue the study, safety and efficacy assessments may be conducted remotely (for example, via telephone), where applicable.

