10.0 Safety Analysis

10.1 General Considerations

No comparisons between treatment groups (Studies M15-566/M15-570) of interest will be performed unless otherwise specified.

All other safety assessments that are taken no more than 45 days after the last dose of study drug will be included in the safety evaluation of the Treatment Period, and all safety assessments that are taken more than 45 days but not more than 20 weeks after the last dose of study drug will be included in the safety evaluation for the Post-treatment Follow-up Visit.

The Safety Data Set will be the data set for all safety data analyses.

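### The only post-treatment analysis window closes on the follow-up visit's own target day, so a scheduled assessment on day 141 or later gets no analysis visit

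*SAP*

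**What the plan says.** **Analysis rules.** SPP 2.2.2 counts RxEnd Day from the last dose (day 0). Treatment-period analyses take observations up to 45 days after that dose. For the follow-up period it says: "Safety observations later than 45 days, but no more than 20 weeks, after the last dose of study drug will be included". One window, Post-Treatment Week 20, is then defined; its lead-in is "For safety assessments that are planned to be collected during post-treatment follow-up period", and it covers RxEnd days above 45 and up to 140. When several observations share a window, "the non-missing observation closest to the nominal day will be used in analyses". The post-treatment final value is "the last non-missing observation greater than 45 days but no more than 20 weeks after the last dose of study drug".

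SAP 10.1 repeats the limits for the follow-up evaluation: "more than 45 days but not more than 20 weeks after the last dose of study drug". Protocol 8.1.4 has the same ceiling; such assessments "will be included in the safety evaluation for the Post-treatment Follow-up Visit".

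**Visit timing.** Protocol Appendix C footnote i reads: "Post-treatment follow-up to occur approximately 20 weeks after the last dose". The Protocol synopsis describes 20 weeks as an approximate minimum for the final follow-up visit. No tolerance is given for this visit; the ±4 days in the Protocol covers Treatment Period visits only. SAP Table 2 footnote k instead counts approximately 20 weeks from the Completion or Premature Discontinuation (PD) visit.

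**What is collected.** The follow-up column of Protocol Appendix C includes clinical laboratory tests, brain MRI and C-SSRS. After premature discontinuation, "safety and efficacy assessments may be conducted remotely (for example, via telephone), where applicable".

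**The concern.** A window for a visit targeted at approximately a given day should have room on both sides of that day. This one has none on the late side. A subject seen one day late has met the Protocol's timing, yet the assessment is too late for the treatment period and too late for the follow-up period. Followed literally, the rule gives a programmer no analysis visit for it.

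Long-term safety is the primary objective. SAP v2.0 has dropped the efficacy, PK and biomarker analyses (SAP 9.1, 11.0 and 12.0), so descriptive safety output is what the abbreviated report contains. The off-drug row of a by-visit safety table is where a reader looks for late findings.

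**Working it through.** **1. Reproduce the bound.** SPP 2.2.2 sets the nominal day at 7 times the visit week, and 7 × 20 = 140. This equals the window's upper limit and the 20-week ceiling in SAP 10.1 and Protocol 8.1.4.

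**2. Room around the target.** Whole days with 45 < RxEnd ≤ 140 run from 46 to 140:

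- days in the window: 140 − 46 + 1 = 95
- room before the target: 140 − 46 = 94
- room after the target: 140 − 140 = 0

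**3. Assignment by day.**

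| RxEnd day | Treatment period (≤ 45) | Follow-up (46 to 140) |
|---|---|---|
| 45 | yes | no |
| 46 | no | yes |
| 140 | no | yes |
| 141 | no | no |

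The open-ended Week 260 window (Rx Days > 1750) does not pick up day 141, because treatment-period analyses stop 45 days after the last dose.

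**4. Comparison with the on-treatment windows.** Late margin = upper bound − nominal day, for every closed window in SPP 2.2.2:

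- laboratory: smallest at Week 12, 126 − 84 = 42 days
- brain MRI: smallest at Week 12, 126 − 84 = 42 days
- body weight and C-SSRS: smallest at Weeks 4 to 48, 7(4n + 2) − 28n = 14 days

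The post-treatment window is the only closed one with a late margin of 0.

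**5. Footnote k.** Target RxEnd day = (PD or Completion visit − last dose) + 140. This exceeds 140 whenever that visit falls after the last dose. For a completer, with last dose at Week 256 and completion at Week 260, it is 28 + 140 = 168, also outside the window. The completer case only illustrates the formula. From the original protocol (09 April 2018) to SPP v2.0 (30 Jul 2021) is 1,208 days, fewer than the 7 × 256 = 1,792 days needed to reach Week 256, and the study ended early.

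**6. How many are affected.** This cannot be derived without a tolerance or observed visit dates. Under an assumed even spread of visits around day 140, the days falling in no period would be 4 of 9 (±4 days), 7 of 15 (±7) or 14 of 29 (±14). The spread and the tolerances are assumptions, not figures from the plan.

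**The case against.** **The ceiling is deliberate and consistent.** Twenty weeks after the last dose appears in Protocol 8.1.4 and 8.1.4.2 to 8.1.4.4, in SAP 10.1 and 10.2, and in the SPP. Protocol 6.1.4 links it to approximately 5 half-lives. This stands in part: the SPP implements the Protocol and is not a programming slip. But the half-life reason is given for adverse event collection, which need not change. It does not explain the visit window. If 140 days is about 5 half-lives, one is about 140 / 5 = 28 days. Day 46 (46 / 28 ≈ 1.6 half-lives) then counts as Post-Treatment Week 20 while day 141 (141 / 28 ≈ 5.0) does not.

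**Day 46 is not an early visit tolerance.** It is where the treatment-period rule ends, so the two periods join without a gap. This stands. The 94 days are not themselves a fault, and the closest-to-nominal rule still prefers the later of two early observations. The fault is the missing late side.

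**COVID-19 deferral.** A reader might infer that pandemic deferral pushes many follow-up assessments past day 140. The Protocol gives this little support. Deferral is to the next onsite visit, and follow-up is the last scheduled visit. Assessments missed at the PD visit would move into follow-up, possibly inside the window.

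**Remote assessment.** It can keep some C-SSRS interviews on time. It cannot supply an MRI scan or a blood sample.

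**Conclusion.** The rule is defective, and the consequence is minor. An assessment that meets the Protocol's approximate timing can fall outside both analysis periods. Under SAP footnote k, the target itself lies outside whenever the PD visit follows the last dose.

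The effect is on descriptive by-visit rows. One is the post-treatment row of the C-SSRS summary (Table 14.3__5), assuming that the by-visit display in SAP 10.4.1 includes follow-up. The others are the MRI-over-time tables, but only if the double-blinded period in SAP 10.4.2, which is not defined, includes follow-up scans. No treatment comparison is shown to change.

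Three stronger readings are not supported:

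- A reader might infer that late follow-up safety data disappear from the report. TEAEs with onset by day 140, deaths and listings are unaffected. Read literally, the PCS laboratory summary (SAP 10.3.1) and the overall C-SSRS summary (SAP 10.4.1) cover the whole study and would include day 141. Protocol 8.1.4.3 limits PCS laboratory values to 20 weeks, but that is a separate inconsistency on which this point does not rely.
- A reader might take the day counts in step 6 of the working to mean that about half of follow-up assessments are lost. The documents give no tolerance and no visit dates, so no share can be stated.
- A reader might infer that post-treatment final values are distorted. No table listed in SPP v2.0 is shown to use them.

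**What to change.** For visit-based assessments (C-SSRS, laboratory, MRI), define Post-Treatment Week 20 as RxEnd Days > 45, state nominal day 140, and keep the existing closest-to-nominal rule. Align the matching sentences in SPP 2.2.2 and SAP 10.1, and record the change in the SAP summary of changes as a departure from Protocol 8.1.4. Leave the 20-week TEAE rule as it is. Aligning the post-treatment final definition would be for consistency only.

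Reconcile SAP Table 2 footnote k with Protocol Appendix C footnote i, since the two count from different dates.

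A fixed late bound would be weaker. Day 154 (140 + 14) would borrow the smallest on-treatment margin, but that margin reflects 28-day visit spacing rather than an acceptable delay, and it could still miss visits timed under footnote k.

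Cost: one window bound, the matching sentences and one line in the summary of changes, with no new data. The downside is that a few assessments made later than 20 weeks enter a descriptive row.
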